2.3. Linkage with Medicare Data

Linkage of the RELIANCE trial to Medicare claims data for a secondary analysis will provide additional information regarding use of the study drugs, the primary outcomes and select secondary outcomes that can be assessed with Medicare data, and will also provide an opportunity to test distributed regression methods with vertically partitioned data. In collaboration with the FDA Office of Medical Policy, the Sentinel SOC will work with the Department of Population Health Sciences (DPHS) at the Duke University to link patients enrolled in the RELIANCE trial to Medicare data. The SOC is located at Harvard Pilgrim Health Care Institute and collaborates with the DPHS on specific Medicare linkage activities. The general process for linkage is described below. A more comprehensive Appendix detailing measures to minimize breaches and protect identifiable data, plans for final disposition of identifiers, and movement of direct identifiers will be submitted to the IRB for review prior to the initiation of data transfer.

The general process for Medicare data linkage will be as follows: The DCC will provide SOC a file with direct patient identifiers (i.e., SSN ± Health Insurance Claims Number (HIC/MBI), date of birth, sex) required for Medicare data linkage. SOC will process these data according to CMS requirements, and will submit this information to CMS via encrypted physical media, or other methods required by CMS (or their designee). CMS then will link trial participants to Medicare enrollment file, create a crosswalk file, and extract the requested Medicare data. CMS will then send the extracted Medicare data files to SOC and the DCC. Finally, the DCC will provide SOC with data from the RELIANCE trial required for the distributed regression methods evaluation. We anticipate using enrollment, inpatient claims, and annual Part D medication dispensing data for RELIANCE trial participants enrolled in Medicare to assess the completeness of ascertainment of the primary outcomes (death or all-cause hospitalization) and evaluate adherence to the assigned treatment. In addition, secondary analyses will evaluate other aspects of healthcare utilization, e.g., urgent care and ED visits.

We will make this data linkage twice. The first linkage will be aligned, where possible, with the trial's interim analysis. The second will occur after the trial is completed, in order to receive Medicare data that covers all or most of the trial follow-up period, given the CMS data release schedule. The interim data request is anticipated to occur in 2022 and to include Annual 2019 and 2020 inpatient claims files, enrollment/death files, and Part D prescription drug dispensing files. The final data request is anticipated to occur in 2023 and to include Annual 2021 inpatient claims files, enrollment/death files, and Part D prescription drug dispensing files, as well as Quarterly

Protocol Version 4.0

2022 (through Q3/2022) inpatient claims files and enrollment/death files. These plans are subject to change, given any changes in Medicare data availability and the trial recruitment timeline.

While the Medicare Quarterly files are not considered final and complete by CMS, ordering these files is the only option for obtaining Medicare data covering the final calendar year of the trial.

2.4. Patient Retention Strategies

Patient retention is critical to the success of any trial and we have incorporated several strategies to enhance retention. First, patient burden is minimized by not requiring in-person follow-up visits and collecting information via brief questionnaires (about 15 minutes) administered online (or by the call center) at 3 and 6 months during first year of enrollment, thereafter, every 6 months until the patient achieves a primary outcome. Second, patients often express pride in participating in an important national study that will potentially help others with similar conditions. In this regard, we will give participants regular newsletters and subscriptions to the COPD Foundation's COPD Digest, which will chronicle the study rationale and progress. The COPD Foundation will not have access to participant identifiers. Participants will only receive these materials if they elect to subscribe to the newsletter. Third, participants endorse that they want to be treated with respect as people rather than "guinea pigs." This involves every step of patient engagement with the study, reinforcing the importance of the participants to the overall study goals and general health of patients with COPD, as well as participation of patients in COPD Foundation social networks that support efforts to improve COPD outcomes.

Protocol Version 4.0

3. Statistical Plan

3.1. Sample Size

RELIANCE is a randomized, pragmatic, comparative effectiveness trial designed to evaluate whether azithromycin is non-inferior to roflumilast in high-risk patients with COPD for prevention of hospitalizations or death. Our choice of a non-inferiority margin of 1.2 was based upon a recently completed clinical trial in COPD, as well as opinions solicited from clinicians and patients^{48,49}. In a survey of 48 clinicians, the minimum clinically important difference was identified to be 1.2 or higher by 75% of the survey participants and the margin of 1.2 was the most commonly selected (33%). An online survey of 50 patients conducted by the COPD PPRN identified a range of different effect sizes, which seemed to vary based on the history of previous COPD exacerbations, and hospitalizations, and tolerance for adverse effects. A margin of 1.2 is within the range of interest expressed by patients. The planned recruitment period is 30 months with an additional 6 months of follow-up. A sample size of 3,200 provides 92% power with a 1-sided type I error of 0.025 to establish non-inferiority based upon a log-rank test with a margin of HR = 1.2 (azithromycin: roflumilast) assuming: (1) the true HR = 1, (2) the cumulative percent with an event at 1 year is 30%, and (3) a 5% loss to follow-up per year (14.3% cumulatively). Post-hoc analyses of trials suggest that while roflumilast appears to benefit both past and current smokers, the benefits of chronic azithromycin may be limited to past smokers.^{34,50} Accordingly, we will monitor treatment outcomes stratified by current vs. former smoking status and present these results to the DSMB to evaluate the relative safety/efficacy of the two treatments. If the lower bound of the 99% CI for azithromycin exceeds 1.5 at any interim analysis, we will recommend to the SC that the current smoking strata be terminated. The sample size of 3,200 participants provides 89% power to detect a heterogeneous effect based upon smoking status (HR = 1 for roflumilast vs HR = 1.538 for azithromycin for current vs former smokers) assuming a reference cumulative incidence of 30% at one year for current smokers in both treatment groups, equal recruitment to all four subgroups, 5% loss to follow-up per year (14.3% cumulatively) and a two-sided type I error rate. These analyses were computed using PASS software and SWOG Statistical tools, respectively.^{51,52}

Protocol Version 4.0

3.2. Analysis Plan

RELIANCE employs a randomized open-label parallel group trial design to evaluate whether azithromycin is non-inferior to roflumilast in high-risk patients with COPD for prevention of hospitalizations or death.

RELIANCE is designed to compare the effectiveness as opposed to pharmacologic efficacy of roflumilast and azithromycin. We will collect data about patient and clinician practices in the study, including the initial and subsequent dosing regimens, adherence, treatment discontinuations, and cross-overs. These practices plus the pharmacologic efficacy of roflumilast and azithromycin in individual patients will contribute to the observed comparative effectiveness of the two treatment options. The primary analysis will therefore be “as randomized” (commonly referred to as intention-to-treat, ITT), secondary sensitive analyses will include per protocol analyses, i.e., the subgroup of patients who adhere to their assigned treatment.

There is considerable debate about the optimal approach to analysis of non-inferiority trials, as randomized or per protocol. The major concern about as randomized analyses for non-inferiority hypotheses is that if a significant number of patients do not adhere to their assigned treatment, the test treatments may falsely appear to have similar effects thereby introducing a bias favoring a conclusion of non-inferiority. Per protocol analyses, which limits the analyses to the subgroup of patients who adhere to their assigned treatment, are recommended for testing non-inferiority hypotheses primarily to avoid this potential bias. However, per protocol analyses of non-inferiority trials have all the same flaws as they do in superiority trials.⁵³ For example, if patients discontinue study assigned treatments because of side effects, the potential decreased effectiveness of the treatment is correctly attributed to the assigned treatment in an as randomized analysis but would not be in a per protocol analysis. The preferred approach is to maintain as randomized ITT as the primary analysis and to institute performance measures that ensure the integrity of the trial and provide essential information for interpretation of the results.⁵⁴ Per protocol analysis will be a key secondary analysis and will be compared with the as randomized analysis. Data on protocol performance such as treatment adherence, losses to follow-up and missing data will be used to help understand and interpret differences, if any, in the results of the two methods.

The primary outcome is the time to first all-cause hospitalization or death. Individuals without an event will be censored at the date of last contact. A Cox proportional hazards model will be used to assess whether azithromycin is non-inferior to roflumilast. Non-inferiority will be achieved if the upper boundary of the confidence interval for the hazard ratio (azithromycin/roflumilast) is

Protocol Version 4.0

less than 1.2, the non-inferiority margin. The level of the confidence interval will be adjusted from 95% to account for type I error spending during interim efficacy analyses and will match the type I error used in the final analysis. If we achieve non-inferiority, then an additional test for superiority will be performed. The primary analysis will adjust for the stratification variables smoking status (current vs former) through the inclusion of a fixed effect and clinic with a random effect, respectively. A key secondary hypothesis is that the treatment effect will differ for current and former smokers. A test of interaction will be used to assess the heterogeneity of treatment effects (HTE) based upon smoking status (current vs former). Secondary analyses will be performed both adjusting for and investigating the HTE for key baseline characteristics including but not limited to 3 pre-specified comparisons: a history of asthma (yes vs no), gender (male vs female) and BMI (obese vs not obese).

Analysis of secondary outcomes by treatment group will employ negative binomial, logistic, linear and Cox proportional hazards models for event rates, binary outcomes, continuous outcomes, and time to event outcomes, respectively. Mixed effects models will be used to model outcomes with repeated measurements over time. Both unadjusted and adjusting models including the stratification variables (clinic and smoking status) as well as clinically important risk factors (e.g. history of asthma, gender, BMI, medication use) will be explored. Summary statistics, model estimates with confidence intervals and p-values will be used to present the findings. A large number of analyses, including HTEs, are planned and caution is necessary in interpreting the results especially since it is generally not possible to pre-specify all potential analyses. The number of secondary analyses explored will be clearly specified and the expected number of false positives will be calculated and included in the presentation of our results. Several methods of adjusting p-values for multiple comparisons exist; however, no clear consensus as to the most appropriate method is available. As recommended by Wang and Lagados, reporting will focus on point estimates and confidence intervals as well as p-values and reports will be considered hypothesis generating.⁴⁴

Performance monitoring is a key component of clinical trials. Our performance monitoring will include site-specific and overall metrics on patient screening, enrollments, retention, missing data, and adherence to treatment. These metrics will be used to assess the internal validity of the trial. External validity will be assessed by evaluation of the characteristics of the screened and enrolled population, the ratio of enrolled to screened participants and comparison of these characteristics to the overall population with COPD. We will rely on published literature as well as CMS data to evaluate the characteristic of US patients with COPD. We will also obtain data from the Master Beneficiary Summary File (via our collaboration with FDA Sentinel).

Protocol Version 4.0

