3.3. Compliance

Compliance will be based upon patient-reported usage. The degree of compliance is an important factor for interpreting the results of the ITT analysis as well as serving the basis for per protocol analyses. However, as noted by Wittes, analyses relying on post-randomization variables are likely to be biased and/or require complex mathematical models with numerous assumptions.⁵⁵

Individuals will be classified according to a number of different methods (e.g. any compliance [at least one usage], minimum compliance [above a certain threshold]) for sensitivity analyses. A variety of causal inference techniques, including inverse probability weighting methods similar to those described by Murray and Hernan, will be used to assess the impact of adherence.⁵⁶ In addition, prescription data will be available for a subset of patients from Medicare claims files via the collaboration with the FDA Sentinel Program. These data will be compared with the self-reported data to help guide the planned compliance analyses.

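### The key secondary per-protocol analysis is set as an adherer subgroup with no adherence window, so its hazard ratio can be biased in either direction when the arms differ in discontinuation

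*Protocol*

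**What the plan says.** Protocol section 3.2 makes the as-randomised analysis primary and describes the alternative as "per protocol analyses, i.e., the subgroup of patients who adhere to their assigned treatment". It explains that such analyses are recommended in non-inferiority trials because non-adherence can make two treatments look falsely alike. It then states: "Per protocol analysis will be a key secondary analysis and will be compared with the as randomized analysis". No period of adherence is given.

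Section 3.3 bases compliance on patient report and calls it the basis for per-protocol analyses. For sensitivity analyses it lists any use and "minimum compliance [above a certain threshold", with no threshold fixed. The same section warns that analyses on post-randomisation variables are likely to be biased, and it plans inverse probability weighting among several causal techniques. It does not say that the weighted result is the key secondary estimate of section 3.2.

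The PICOTS table and sections 2.2 and 2.4 stop the patient questionnaires once a primary outcome is recorded.

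**The concern.** Membership of the subgroup depends on what happens after randomisation, and the time available to become non-adherent depends on the outcome. A patient hospitalised in week 3 has had almost no chance to stop and stays in. An event-free patient who stops at month 10 is removed, with all the event-free time. This raises the apparent hazard in each arm, and raises it more in the arm that stops more. Prognosis need play no part.

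The protocol uses the contrast between this analysis and ITT to judge whether non-adherence has diluted the ITT result (sections 3.2 and 3.4). If the contrast carries a bias of its own, agreement does not reassure and disagreement does not alarm.

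**Working it through.** **Inputs from the protocol.** Section 3.1: "Our choice of a non-inferiority margin of 1.2 was based upon a recently completed clinical trial in COPD"; "A sample size of 3,200 provides 92% power with a 1-sided type I error of 0.025 to establish non-inferiority based upon a log-rank test"; a true HR of 1 for power; "the cumulative percent with an event at 1 year is 30" (percent); and "a 5% loss to follow-up per year (14.3% cumulatively" (percent). Recruitment is 30 months plus 6 months of follow-up, allocated 1:1. Section 3.5: 1368 expected events and a final two-sided level of 0.04695.

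**Reproducing the plan's own figures.**
- Event hazard: −ln(0.70) = 0.3567 per year. Loss hazard: −ln(0.95) = 0.0513 per year; 1 − 0.95³ = 14.3%.
- With s = 0.3567 + 0.0513 = 0.4080 and uniform censoring between 0.5 and 3 years, P(event) = (0.3567/s) × [1 − (e^(−0.5s) − e^(−3s))/(2.5s)] = 0.4273. Then 3,200 × 0.4273 = 1367.5, against 1368 stated.
- Power = Φ(√(1368/4) × ln 1.2 − 1.96) = Φ(1.41) = 0.921, against 92% stated.

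Both reproduce, so the same event, loss and accrual model is used below.

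**Assumption.** The protocol gives no expected discontinuation rates for this trial. I assumed exponential stopping, independent of prognosis and without effect on the hazard afterwards, and varied the rates.

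**Mechanism by hand.** Under full adherence, a patient whose follow-up ends at time t stays in with probability (1 − yearly stopping rate)^t.
- Roflumilast at 35% per year: week 3, 0.65^(3/52) = 0.975; two event-free years, 0.65² = 0.423; ratio 2.3.
- Azithromycin at 26% per year: week 3, 0.74^(3/52) = 0.983; two event-free years, 0.74² = 0.548; ratio 1.8.

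Early events are over-represented in both arms, and more so in the arm that stops more.

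**Large-sample simulation at true HR 1.20** (one to two million patients per scenario, Cox model on treatment). For the 12-, 6- and 3-month windows, a patient is excluded only for stopping inside the window while still event-free and under follow-up.

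| Yearly stopping, azithromycin / roflumilast | Analysis | HR |
|---|---|---|
| 26% / 35% | adherent throughout | 1.08 |
| 26% / 35% | on drug for at least 80% of own follow-up | 1.10 |
| 26% / 35% | adherent through 12 months | 1.15 |
| 26% / 35% | adherent through 6 months | 1.19 |
| 26% / 35% | adherent through 3 months | 1.19 to 1.20 |
| 35% / 26% | adherent throughout | 1.30 to 1.31 |
| 26% / 26% | adherent throughout | 1.18 to 1.19 |
| all of the above | all patients, censored at stopping | 1.20 |

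**At trial size** (3,200 patients, 1,000 trials per scenario, true HR 1.20, confidence level matching 0.04695), the chance that the upper limit falls below 1.2:

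| Stopping, azithromycin / roflumilast | Adherent throughout: HR | Chance |
|---|---|---|
| 20% / 20% | 1.19 | 3.6% |
| 26% / 26% | 1.19 | 4.1% |
| 5% / 15% | 1.09 | 39% |
| 20% / 30% | 1.07 | 47% |
| 26% / 40% | 1.01 | 79% |
| 26% / 15% | 1.32 | 0% |
| 33% / 15% | 1.42 | 0% |

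In the same data ITT gives 1.20 and 2.7%. Across all scenarios run, censoring everyone at discontinuation gives 1.20 and 2.1 to 3.3%, and excluding only those who stop within 3 months gives 1.18 to 1.21 and 2.1 to 4.4%. Monte Carlo error is about 0.5 points near 2.5% and at most 1.6 points elsewhere.

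**Which arm stops more?** The protocol's own figures do not settle it.
- Azithromycin: 26% (section 1.1) or 33% (section 4.3), but 9% and 5% in the two smaller trials.
- Roflumilast: 15% or 12% (section 4.3), but 24.6% all-cause at only 12 weeks when started at full dose (section 1.1). For the lower start, the odds ratio of 0.66 gives odds 0.66 × 0.246/0.754 = 0.215, or 17.7%.

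These figures come from different trials, durations and reasons for stopping, and support either sign.

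**The case against.** The strongest reply is that nothing in the protocol requires adherence until the event or censoring. A reader might infer that from the word adhere and from the questionnaires stopping at the event, but sections 3.2 and 3.3 leave the window open. Under the any-use rule both example patients stay in and the problem disappears; with a 3-month window it nearly does. This stands, and so the size of the bias is conditional. It does not remove the point: an 80% threshold or a 12-month window, both ordinary choices, still gives 1.10 or 1.15, and the protocol rules out neither.

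A reader might also infer that the analysis will favour azithromycin and so falsely support non-inferiority. The documents do not support that. It needs more stopping on roflumilast; more stopping on azithromycin pushes the HR upwards.

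The protocol also acknowledges the general weakness. Section 3.2 says per-protocol analyses carry the flaws they have in superiority trials, and section 3.3 warns of bias and plans weighting. This stands as well. But the flaw illustrated in 3.2 is that side-effect stopping is no longer charged to the drug, which is a different mechanism, and the weighting is not tied to the estimate that 3.2 sets beside ITT. The statistical analysis plan, not shown, may fix the window. The choice of an adherer subgroup, however, is made in the protocol.

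Two further reservations hold. Treatment data do not come only from questionnaires: Table 3 adds claims, and section 2.2 adds site reports of medication changes, though section 3.3 bases compliance on patient report. And simple censoring returns 1.20 here because stopping was simulated as unrelated to prognosis. The weights themselves were not tested, nor was dilution of ITT.

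**Conclusion.** The concern holds in a limited form. The protocol fixes its key secondary per-protocol analysis as a subgroup chosen on post-randomisation adherence, without a window. If adherence must be sustained, the HR is biased whenever discontinuation differs between arms. At a true HR of 1.20 and a nine-point difference in yearly stopping (26% against 35%), the estimate is about 1.08 to 1.15 when roflumilast is stopped more. With those rates reversed, full adherence gives about 1.31. The bias is small when stopping is equal or when only early stopping excludes.

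The stopping rates are assumptions, taken as constant over time and independent of prognosis. The direction in this trial cannot be known from the documents.

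A reader might conclude that the trial's main result is at risk. It is not: ITT alone decides non-inferiority, and no decision rule uses the per-protocol HR. What is weakened is the check on whether ITT was diluted. This should be fixed, but it is not a condition for the primary analysis to be valid.

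**What to change.** In section 3.2, define the key secondary per-protocol estimate as follows: all randomised patients, followed from randomisation, censored at discontinuation of assigned treatment or crossover, with the inverse probability weighting already planned in section 3.3. The weight model should include baseline predictors of stopping (such as smoking status and site) and time-varying ones (such as reported adverse events, PROMIS scores and weight). Label any adherer-subgroup analysis descriptive, and state its adherence window if it is kept.

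The cost is a change of wording and modest programming; the method and these variables are already in the plan. The downside is reliance on measured predictors of stopping: if stopping depends on unmeasured prognosis, the weighted estimate remains biased. Censoring without weights was shown unbiased only when stopping is independent of prognosis, so the weights should not be dropped. Contacts are at 1 week, 3 and 6 months and then every 6 months, so the date of stopping, and not only the fact of it, needs to be captured or its approximation stated.
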